5.1 Imputation rules

5.1.1 Study drug

No imputation of missing/partial start date of study drug. If missing the time of study drug end date will be imputed to 23:59:59.

5.1.2 AE date imputation

Rules for imputing the AE end date:

- If the AE end date month is missing, the imputed end date should be set to the earliest of the (study end date, 31DECYYYY, date of death).
- If the AE end date day is missing, the imputed end date should be set to the earliest of the (study end date, last day of the month, date of death).
- If AE year is missing, the end date will not be imputed.

Rules for imputing the AE start date:

- If imputing end dates, this should be done prior to calculating imputed start dates

The following table explains the notation used in the logic matrix. Please note that **missing start dates** will not be imputed.

	Day	Month	Year
Partial Adverse Event Start Date	Not used	MON	YYYY
Treatment Start Date	Not used	TRTM	TRTY

The following matrix explains the logic behind the imputation.

	MON MISSING	MON < TRTM	MON = TRTM	MON > TRTM
YYYY MISSING	(1) No convention	(1) No convention	(1) No convention	(1) No convention
YYYY < TRTY	(2.a) Before Treatment Start	(2.b) Before Treatment Start	(2.b) Before Treatment Start	(2.b) Before Treatment Start
YYYY = TRTY	(4.a) Uncertain	(4.b) Before Treatment Start	(4.c) Uncertain	(4.c) After Treatment Start
YYYY > TRTY	(3.a) After Treatment Start	(3.b) After Treatment Start	(3.b) After Treatment Start	(3.b) After Treatment Start

Before imputing AE start date, find the AE start reference date.

1. If the (imputed) AE end date is complete and the (imputed) AE end date < treatment start date then AE start reference date = min(informed consent date, earliest visit date).
2. If (imputed) AE end date is complete and (imputed) AE end date >= Treatment period 1 start date i.e. TR01SDT but before Extension Treatment start date i.e. TR02SDT (or Extension Treatment start date is missing) then AE start reference = treatment period 1 start date i.e. TR01SDT.
3. Else if (AE start year > Extension Treatment start year) or (AE start year = Extension Treatment start year and AE start month >= Extension Treatment start month) then AE start reference = Treatment Period 2 start date i.e. TR02SDT. Else AE start reference = Treatment Period 1 start date i.e. TR01SDT.

Impute AE start date

1. If the AE start date year value is missing, the date uncertainty is too high to impute a rational date. Therefore, if the AE year value is missing, the imputed AE start date is set to NULL.
2. If the AE start date year value is less than the treatment start date year value, the AE started before treatment. Therefore:
 - a. If AE month is missing, the imputed AE start date is set to the mid-year point (01JulYYYY).
 - b. Else if AE month is not missing, the imputed AE start date is set to the mid-month point (15MONYYYY).

3. If the AE start date year value is greater than the treatment start date year value, the AE started after treatment. Therefore:
 - a. If the AE month is missing, the imputed AE start date is set to the year start point (01JanYYYY).
 - b. Else if the AE month is not missing, the imputed AE start date is set to the later of (month start point (01MONYYYY), AE start reference date + 1 day).
4. If the AE start date year value is equal to the treatment start date year value:
 - a. And the AE month is missing the imputed AE start date is set to the AE reference start date + 1 day.
 - b. Else if the AE month is less than the treatment start month, the imputed AE start date is set to the mid-month point (15MONYYYY).
 - c. Else if the AE month is equal to the treatment start date month or greater than the treatment start date month, the imputed AE start date is set to the later of (month start point (01MONYYYY), AE start reference date + 1 day).

If complete (imputed) AE end date is available and the imputed AE start date is greater than the (imputed) AE end date, then imputed AE start date should be set to the (imputed) AE end date.

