8.2 Data collection

Designated investigator staff will enter the data required by the protocol into the OC/RDC system. Designated investigator site staff will not be given access to the system until they have been trained. Data from both the core study (CQGE031C2201) and extension study (CQGE031C2201E1) will be entered into the same database.

Automatic validation procedures within the system check for data discrepancies during and after data entry and, by generating appropriate error messages, allow the data to be confirmed or corrected online by the designated investigator site staff. The investigator must certify that the data entered into the electronic Case Report Forms are complete and accurate. After database lock, the investigator will receive copies of the patient data for archiving at the investigational site.

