2.5.1 Adverse events

All adverse events which start after the first dose of study medication in the extension study and within 16 weeks of last dose, or events present prior to the first dose of extension study treatment

and increased in severity (within 16 weeks of last dose), will be considered as a treatment emergent adverse events. Treatment emergent adverse events (TEAEs) will be presented overall (including those that started during treatment and follow-up epoch) and those which started during the treatment epoch. Non-TEAEs will be presented for those which started during the follow-up epoch.

Adverse events that started during the core study were reported and analyzed in the core study and will not be included in tables of the extension study unless they become more severe. They will, however, be included in listings with additional collected information (e.g., outcome) as applicable.

Adverse events that started in the core study but became more severe in the extension study will be reported and analyzed as new events.

Treatment emergent adverse events with the number and percentage of patients having any adverse event by system organ class (SOC) and preferred term (PT) will be provided for:

- All adverse events
- Adverse events by maximum severity
- Adverse events suspected by the investigator as study drug-related
- Serious adverse events
- Adverse events leading to permanent discontinuation of study drug (only for treatment epoch)

Also, a separate summary table for most frequently reported TEAEs during the study, by SOC and PT, will be produced. Most frequent TEAEs will be those with their PT representing at least 5% of subjects.

Clinicaltrials.gov and EudraCT

For the legal requirements of ClinicalTrials.gov and EudraCT, two required tables on <on-treatment/treatment emergent> adverse events which are not serious adverse events with an incidence greater than 5% and on <on-treatment/treatment emergent> serious adverse events and SAE suspected to be related to study treatment, will be provided by system organ class and preferred term on the safety set population.

If for a same patient, several consecutive AEs (irrespective of study treatment causality, seriousness and severity) occurred with the same SOC and PT:

- a single occurrence will be counted if there is ≤ 1 day gap between the end date of the preceding AE and the start date of the consecutive AE

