2.5.5 Statistical model, hypothesis, and method of analysis

No hypotheses will be tested as per the protocol. All the analysis will have a descriptive purpose.

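### An adverse event with only a start year, falling in the year the extension began, is dated on or before the first extension dose and so drops out of the treatment-emergent tables unless it worsens

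*SAP*

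**What the plan says.** SAP 5.1.2 works in two stages. It first chooses a reference date, then imputes the start.

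- **Reference step 2** covers AEs with an "AE end date >= Treatment period 1 start date i.e. TR01SDT but before Extension Treatment start date i.e. TR02SDT", and uses the first core dose, TR01SDT.
- **Reference step 3** uses TR02SDT if the AE year is later than the extension start year, or if the years match and the AE month is at or after the extension start month. Otherwise: "Else AE start reference = Treatment Period 1 start date i.e. TR01SDT".
- **Rule 3.a** (AE year after the treatment start year): "If the AE month is missing, the imputed AE start date is set to the year start point (01JanYYYY").
- **Rule 3.b** (same, month known): "Else if the AE month is not missing, the imputed AE start date is set to the later of (month start point (01MONYYYY") and the reference date plus one day.
- **Rule 4.a** (AE year equal to the treatment start year): "And the AE month is missing the imputed AE start date is set to the AE reference start date + 1 day".
- **Closing step:** if the imputed start falls after the end date, it is reset to the end date, so this step can only move the start earlier.

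SAP 2.5.1 counts an AE as treatment-emergent if it starts after the first extension dose and within 16 weeks of the last dose, or was already present and worsened in that window. AEs that began in the core study "will not be included in tables of the extension study unless they become more severe".

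**The concern.** Reference step 3 needs a month to select TR02SDT in the extension start year, and a year-only date has none. The end date is compared with TR02SDT only to pick out AEs that finished before it. Nothing brings back an AE that is still ongoing or finishes later. Rule 3.a then lacks the floor that rule 3.b has.

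Losing the month therefore reverses the treatment of the AE. Where only the day is missing and the month is the extension start month, the SAP takes the cautious line and counts the AE as on treatment. Where the month is missing too, it assigns the AE to the core period, although much of the year may lie after the first extension dose.

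The treatment-emergent tables (all AEs, severity, relatedness, seriousness, discontinuation) carry the primary objective, and any error runs one way, towards undercounting. The follow-up tables of non-treatment-emergent AEs would not catch these records, because the imputed start precedes that epoch. SAP section 4 also contains a treatment-emergent definition without the 16-week limit. It still needs onset after the first extension dose or worsening, so it does not help either.

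**Working it through.** **Inputs.** The rules are those of SAP 5.1.2. The shortest gap from TR01SDT to TR02SDT comes from the protocol: Visit 203 at Week 32 (section 4.1) plus 14 days to Visit 301 (section 3.1), so 32 × 7 + 14 = 238 days. The longest gap is not stated and is assumed below. The plan gives no figure of its own to reproduce.

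**Meaning of treatment start date.** The AE rules do not define it. TR01SDT is the more natural reading: if it were TR02SDT, reference step 1 would take every case meant for step 2, and the medication rules in 5.1.3 name TR01SDT. Both readings were checked.

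**Worked example, different years.** TR01SDT 15Jun2016, TR02SDT 20Feb2017, AE start year 2017 only, AE end 30Nov2017.

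1. Steps 1 and 2 do not apply, because the end date is after TR02SDT.
2. Step 3: 2017 is not later than 2017, and the month test cannot be met. The reference is TR01SDT.
3. Reading TR01SDT: 2017 > 2016, so rule 3.a gives 01Jan2017, which is 50 days before the first extension dose.
4. Reading TR02SDT: the years are equal, so rule 4.a gives 15Jun2016 + 1 = 16Jun2016, outside the recorded AE year.
5. Same AE recorded as Feb2017: the month test is met and the reference is TR02SDT. The later of 01Feb2017 and 21Feb2017 is 21Feb2017, which is treatment-emergent.

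Possible onset days run from 1 January to 30 November, 334 in all. Days after 20 February: 334 − 51 = 283, or 283/334 = 85%.

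**Worked example, same year.** TR01SDT 15Jan2016, TR02SDT 20Sep2016, AE year 2016 only, ongoing. The reference is TR01SDT and rule 4.a gives 16Jan2016. Recorded as Sep2016, it becomes 21Sep2016.

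**All plausible dates.** The rules were coded as written and run over 730 core start dates × 189 gaps (238 to 426 days, upper end assumed) = 137,970 pairs. The AE was ongoing, ending on TR02SDT, or ending 30 or 200 days later.

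| Case (reading TR01SDT) | Pairs | Imputed start | After TR02SDT |
|---|---|---|---|
| Start years differ | 121,655 | 01 January (3.a) | 0 |
| Same start year | 16,315 | TR01SDT + 1 (4.a) | 0 |

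The count is also 0 of 137,970 under the TR02SDT reading. The imputed date equals the first dose only if that dose was on 1 January. Rule 3.a governs 121,655/137,970 = 88% of pairs here. It governs 78% on a narrower grid of 33,580 pairs (365 start days × 92 gaps, 238 to 329 days), so this share depends on the assumed gap; the zero does not.

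**Calendar days exposed.** With first doses spread evenly over a 365-day year, the days left in that year average (0 + 1 + … + 364)/365 = 182. The treatment-emergent window for a full course is 336 days to the Week 48 dose + 112 = 448 days, and 182/448 = 41%. This is the window in which such a record could arise, not a rate of lost AEs.

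**Effect per record.** At most one patient in a preferred-term row: 1/240 = 0.4 percentage points.

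**The case against.** The strongest reply is that such records may hardly exist. AEs are sought at every visit, treatment visits are four weeks apart, start and end dates are collected, and incomplete data are queried before lock. A site can normally supply the month. The documents give no count, so the effect could be zero. This stands, and it limits the weight of the point.

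Second, rule 3.a read against the core start does what its label says, since 1 January is after core treatment began; the common cause is reference step 3. That is fair on cause, but changing step 3 alone leaves 1 January in place whenever the start years differ, so both need editing. A program that counted a missing month as meeting the test and also took TR02SDT as treatment start would date ongoing and later-ending AEs correctly. The SAP says neither.

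Third, the percentages above are illustrative. They rest on assumed gaps, even spacing of first doses, or one invented patient. This also stands.

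Fourth, consequences are limited: "No hypotheses will be tested as per the protocol", and these AEs remain in the general listings, the adjudicated-event listings and the death reports. True, but the summary tables are what readers will use for incidence.

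**Conclusion.** The concern holds, as a minor point. Under the literal rules and either reading of treatment start date, every year-only AE in the extension start year that is ongoing or ends on or after TR02SDT is dated on or before the first extension dose. It is therefore not treatment-emergent by onset. That conclusion is about the text and needs no assumption on record counts.

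The size of any undercount cannot be determined from the documents and is probably small. Each record removes at most one patient from a preferred-term row, and overall incidence does not move if that patient has another treatment-emergent AE.

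**What to change.** Make three edits to SAP 5.1.2.

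1. **Reference step 3:** add that the reference is TR02SDT when the AE year equals the extension start year, the month is missing, the (imputed) end date is missing or on or after TR02SDT, and the AE was not already recorded and reported in the core study.
2. **Rule 3.a:** use the later of 1 January of the AE year and the reference date plus one day, matching rule 3.b.
3. **Treatment start date:** give it one meaning throughout the section, consistent with steps 1 and 2 (TR01SDT).

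On the 33,580-pair grid, edits 1 and 2 moved every ongoing year-only AE to after TR02SDT. None of 58,935 test records ending before TR02SDT changed, and none of 42,700 with a known month or a later year. An AE ending on the first dose day itself is reset to that day by the closing step and stays non-emergent, which is harmless; the text should say so.

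The core-study check should be feasible: "Data from both the core study (CQGE031C2201) and extension study (CQGE031C2201E1) will be entered into the same database". How it is applied needs stating, particularly for AEs arising between consent at Visit 206 and the first dose at Visit 301.

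The cost is a few lines of text and code. The downside is that an occasional core-period AE not recorded there may be counted in the extension. This matters most when both studies began in one calendar year, where at most about 365 − 239 = 126 days of that year follow the first extension dose.

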5.1.3 Concomitant medication date imputation

No imputation of numeric date will be performed for the dates of medication recorded on the Trial Rescue Medication CRF page or the Prior urticaria therapy CRF page. All therapies on the Prior urticaria therapy CRF page will be considered as prior.

Rules for imputing the concomitant medication (CM) end date (including on-going records):

- If imputing end dates, this should be done prior to calculating imputed start dates.
 - When the medication is on-going at the end of the study, no numeric end date is derived.
 - If the end date is completely missing no numeric end date is derived.
- a) If CM end day is missing and CM month/year are non-missing, then impute CM date as the minimum of study end date and the last day of the month.
 - b) If CM end day/month are missing and CM year is non-missing, then impute CM date as the minimum of study end date and the end of the year (31DECYYYY).
 - c) If imputed CM end date is less than the complete CM start date, use the complete CM start date as the imputed CM end date.

Rules for imputing the CM start date:

- If imputing end dates, this should be done prior to calculating imputed start dates.

The following table explains the notation used in the logic matrix.

	Day	Month	Year
Partial CM Start Date	Not used	MON	YYYY
Treatment Start Date	Not used	TRTM	TRTY

The following matrix explains the logic behind the imputation.

	MON MISSING	MON < TRTM	MON = TRTM	MON > TRTM
YYYY MISSING	(1) Uncertain	(1) Uncertain	(1) Uncertain	(1) Uncertain
YYYY < TRTY	(2.a) Before Treatment Start	(2.b) Before Treatment Start	(2.b) Before Treatment Start	(2.b) Before Treatment Start
YYYY = TRTY	(4.a) Uncertain	(4.b) Before Treatment Start	(4.a) Uncertain	(4.c) After Treatment Start
YYYY > TRTY	(3.a) After Treatment Start	(3.b) After Treatment Start	(3.b) After Treatment Start	(3.b) After Treatment Start

1. If the CM start date year value is missing, the imputed CM start date is set to one day prior to *Treatment start date (TR01SDT)*.
2. If the CM start date year value is less than the *Treatment start date (TR01SDT)* year value, the CM started before treatment. Therefore:
 - a) If the CM month is missing, the imputed CM start date is set to the mid-year point (01JulYYYY).
 - b) Else if the CM month is not missing, the imputed CM start date is set to the mid-month point (15MONYYYY).
3. If the CM start date year value is greater than the *Treatment start date (TR01SDT)* year value, the CM started after treatment. Therefore:
 - a) If the CM month is missing, the imputed CM start date is set to the year start point (01JanYYYY).
 - b) Else if the CM month is not missing, the imputed CM start date is set to the month start point (01MONYYYY).
4. If the CM start date year value is equal to the *Treatment start date (TR01SDT)* year value:
 - a) And the CM month is missing or the CM month is equal to the *Treatment start date (TR01SDT)* month, then the imputed CM start date is set to one day prior *Treatment start date (TR01SDT)*.
 - b) Else if the CM month is less than the *Treatment start date (TR01SDT)* month, the imputed CM start date is set to the mid-month point (15MONYYYY).
 - c) Else if the CM month is greater than the *Treatment start date (TR01SDT)* month, the imputed CM start date is set to the month start point (01MONYYYY).

If complete (imputed) CM end date is available and the imputed CM start date is greater than the complete (imputed) CM end date, then imputed CM start date should be set to the complete (imputed) CM end date.

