Family Malignancy history	D	-	-	-	-	-	-	-	-	-	-	-	-	-	-	-	-	-	-	
Ongoing Concomitant medication usage	D	D	D	D	D	D	D	D	D	D	D	D	D	D	D	D	D	D	D	
Surgery and procedures	D	D	D	D	D	D	D	D	D	D	D	D	D	D	D	D	D	D	D	
Dispense H1-AH rescue medication	-	S	S	S	S	S	S	S	S	S	S	S	S	S	S	S	S	S	S	
Rescue medication usage	-	D	D	D	D	D	D	D	D	D	D	D	D	D	D	D	D	D	D	
Dispense epinephrine	-	S	-	-	-	-	-	-	-	-	-	-	-	-	-	-	-	-	-	
Study drug administration	-	D	D	D	D	D	D	D	D	D	D	D	D	D	-	-	-	-	-	
Contact IRT	DS	DS	DS	DS	DS	DS	DS	DS	DS	DS	DS	DS	DS	DS	-	-	-	-	DS	

Epoch	Core study *, 1, a	Treatment Epoch													Post-treatment follow up epoch				
Visit	206	301	302	303	304	305	306	307	308	309	310	311	312	313 PSW	401	402	403	404	405 PSW
Week	-3/-2	1	4	8	12	16	20	24	28	32	36	40	44	48	52	64	76	88	100
Day	-21/-14	1	29	57	85	113	141	169	197	225	253	281	309	337	365	449	533	617	701
Patient eDiary																			
UPDD	DS	DS	DS	DS	DS	DS	DS	DS	DS	DS	DS	DS	DS	DS	DS	DS	DS	DS	DS
Laboratory tests/ Safety																			
Stool ova and parasite evaluation	DS	-	-	-	-	-	-	-	-	-	-	-	-	-	DS	-	-	-	-
Blood sample	Hematology	DS	DS	DS	DS	DS	DS	DS	DS	DS	DS	DS	DS	DS	DS	DS	DS	DS	DS
	Clinical Chemistry including bilirubin, hsCRP	DS	DS	DS	DS	DS	DS	DS	DS	DS	DS	DS	DS	DS	DS	DS	DS	DS	DS

Epoch		Core study *, 1, a	Treatment Epoch												Post-treatment follow up epoch					
Visit		206	301	302	303	304	305	306	307	308	309	310	311	312	313 PSW	401	402	403	404	405 PSW
Week		-3/-2	1	4	8	12	16	20	24	28	32	36	40	44	48	52	64	76	88	100
Day		-21/-14	1	29	57	85	113	141	169	197	225	253	281	309	337	365	449	533	617	701
Urine sample	Urinalysis dipstick (if abnormal submit sample to central lab)	D	D	-	-	-	D	-	-	-	D	-	-	-	D	-	-	D	-	D
	Pregnancy test	D	D	D	D	D	D	D	D	D	D	D	D	D	D	D	D	D	D	D
Physical Exam		S	S	S	S	S	S	S	S	S	S	S	S	S	S	S	S	S	S	S
Vital signs		D	D	D	D	D	D	D	D	D	D	D	D	D	D	D	D	D	D	D
Weight		D	-	-	-	-	-	-	-	-	-	-	-	-	-	-	-	-	-	D
ECG		D	-	-	-	-	-	-	-	-	-	-	-	-	D	-	-	-	-	D
Adverse events		D	D	D	D	D	D	D	D	D	D	D	D	D	D	D	D	D	D	D
Liver safety monitoring		D	D	D	D	D	D	D	D	D	D	D	D	D	D	D	D	D	D	D
Renal safety monitoring		D	D	D	D	D	D	D	D	D	D	D	D	D	D	D	D	D	D	D

Epoch	Core study *, 1, a	Treatment Epoch												Post-treatment follow up epoch					
		206	301	302	303	304	305	306	307	308	309	310	311	312	313 PSW	401	402	403	404
Visit	206	301	302	303	304	305	306	307	308	309	310	311	312	313 PSW	401	402	403	404	405 PSW
Week	-3/-2	1	4	8	12	16	20	24	28	32	36	40	44	48	52	64	76	88	100

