2.6.3 The weekly Urticaria Activity Score (UAS7)

[figure not shown]
The UAS7 is the sum of the HSS7 score and the ISS7 score. The weekly UAS7 score will then range from 0 to 42. Complete UAS7 response is defined as $UAS7 = 0$.

[figure not shown]
Changes from baseline in UAS7 score will be computed and will be summarized along with the absolute values at each visit. Mean with 95% confidence interval will be displayed graphically over time to describe the score change during the study. In addition, UAS7 descriptive statistics will be summarized, [REDACTED].

[figure not shown]
UAS7=0 response will be summarized and plotted by visit and response rate with the 95% Clopper-Pearson exact confidence interval will be included in the analysis. In addition, achievement of UAS7 ≤ 6 will be summarized similarly. Also, UAS7=0 response will be summarized, [REDACTED].

Kaplan-Meier estimates of the time to first UAS7=0 response and of the time to first loss of response for patients having achieved response at Week 52, will be plotted and will be tabulated at defined time points. In addition, Kaplan-Meier estimates of the time to first UAS7 > 6 for patients having achieved UAS7 ≤ 6 at Week 52 [REDACTED], will be tabulated at defined time points.

For patients with concomitant use of omalizumab, UAS scores will be censored at the date of start of omalizumab and treated as missing onward.

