For the response rate analysis, for patients with missing data either due to discontinuation or due to insufficient eDiary data during that week or the start concomitant use of omalizumab, data imputation of the response will be done using the worst-case scenario (i.e. non-responder). For the patients completing the study, there will be no more imputation applied after the end of study visit. For the patients discontinuing the study early or start concomitant use of omalizumab, the imputation will be applied up to Week 100.

Duplicate data handling of questionnaires

For HSS7, ISS7 and UAS7, the daily score is derived from the average of morning and evening scores. All other questionnaires are completed either daily or at visits. If any of those questionnaires are completed more than once per day or visit (depending on the questionnaire schedule), then the worst outcome (i.e. the highest score) of the duplicate observations will be used in the analysis.

Censoring of time to response.

Time endpoints, such as time to first complete hives response, will be considered censored at the date of the last non-missing weekly score up to E1 Week 52, for any non-responder.

Censoring of time to loss of response.

For any patient maintaining response, the time to loss, such as time to first loss of complete hives response for patients who completed the treatment epoch and achieved complete hives response at Week 52, will be considered censored at the date of the last non-missing weekly score or at the date of start concomitant use of omalizumab.

Note that time to loss of response will be missing for all patients without having achieved the response in the E1 treatment period at study week 52.

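### SAP 5.1.3 sets no lower bound on an imputed omalizumab start date, so a partly dated post-treatment start could move the efficacy cut-off to before omalizumab was given

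*SAP*

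**What the plan says.** **The cut-off.** SAP 2.6.3 says that for patients taking omalizumab "UAS scores will be censored at the date of start of omalizumab and treated as missing onward". SAP 2.6.1 and 2.6.2 say the same for HSS and ISS. In response rates, SAP 2.6.10 counts the resulting missing weeks as non-response: "For the patients discontinuing the study early or start concomitant use of omalizumab, the imputation will be applied up to Week 100". Time to loss of response is censored at the omalizumab start, and is missing for anyone without the response at Week 52. Section 2.6.10 reports 17 patients on omalizumab and places their use after treatment.

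**The date rules (SAP 5.1.3).**
- Year missing (rule 1): "If the CM start date year value is missing, the imputed CM start date is set to one day prior to" TR01SDT.
- Year later than that of TR01SDT, month missing (rule 3a): "If the CM month is missing, the imputed CM start date is set to the year start point (01JanYYYY".
- Year later than that of TR01SDT, day missing (rule 3b): "Else if the CM month is not missing, the imputed CM start date is set to the month start point (01MONYYYY".

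SAP 5.1.2 shows what the variables mean: "Treatment period 1 start date i.e. TR01SDT but before Extension Treatment start date i.e. TR02SDT". TR01SDT is therefore the first core-study dose. Only the rescue-medication and prior-urticaria-therapy CRF pages are exempt from imputation; omalizumab is not named.

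**A second cut-off.** SAP Section 4 censors efficacy at the last visit before omalizumab began, not at the start date.

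**The concern.** A date rule that is harmless for a medication listing matters more once the date is an efficacy cut-off. Rule 3 can place a start known to be post-treatment inside the treatment epoch, and rule 1 places it before the core study. Scores obtained without omalizumab would then be discarded.

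The consequences differ by analysis. Score summaries lose data. Weekly response rates gain non-responders. If the Week 52 score is cut, the patient leaves the group in which sustained remission, the only stated secondary objective, and time to loss are assessed. If only the day is missing and response was first lost in the deleted days, that loss becomes a censored time.

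**Working it through.** The plan gives no figure for this effect, so there is none to reproduce. The rules were applied literally.

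**Inputs**
- Earliest roll-over at core Week 32 (Protocol 4.1); first extension dose about 14 to 21 days after Visit 206 (Protocol 3.1).
- Week 52 visit on Day 365, Week 100 on Day 701 (SAP Table 1-1); study week w covers Days 7(w−1)+1 to 7w (SAP Table 1-2).
- 17 omalizumab patients (SAP 2.6.10); about 240 patients expected (Protocol 9.7).
- Assumptions: true starts spread evenly over Days 365 to 701, for every extension Day 1 in one calendar year.

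**1. Which rule applies.** First core dose to first extension dose: at least 32 × 7 + 14 = 238 days. To extension Day 365: 238 + 364 = 602 days. That exceeds one year, so a start from Day 365 always falls in a later calendar year than TR01SDT. Rule 3 applies whenever the year is known.

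**2. Size of the shift** (true start minus imputed start)

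| Missing part | Imputed start | Shift, days | Mean | Imputed before Day 365 |
|---|---|---|---|---|
| Day | first of month | 0–30 | 14.7 | 4% |
| Month | 1 January | 0–364 (365 in a leap year) | 182 | 54% |
| Year | TR01SDT − 1 day | to at least 239 days before extension Day 1 | – | all |

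The means correspond to about 14.7/7 ≈ 2 and 182/7 = 26 weekly scores.

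**3. Example.** Extension Day 1 is 1 March 2017 and omalizumab starts on 15 November 2018 (Day 625, Week 90). Recorded as 2018 only, it becomes 1 January 2018 (Day 307, Week 44). The loss is 625 − 307 = 318 days, including Week 52 (Days 358–364). Recorded as November 2018, it becomes 1 November and the loss is 14 days.

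**4. Does the reference date matter?** With TR02SDT (extension start) in place of TR01SDT, 0.0% of month-missing or day-missing dates change for starts from Day 365. With the year missing, the date becomes Day −1, and all post-baseline extension scores are still cut.

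**5. Effect on a weekly response rate.** Each patient turned from responder to non-responder costs 1/240 = 0.42 percentage points. For 0 to 17 such patients the range is 0 to 17/240 = 7.1 points. The upper end needs all 17 to be partly dated, cut at that week, and otherwise responders.

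**6. What a floor does.** A floor at Day 365 protects all treatment-epoch data and lowers the mean month-missing shift from 182 to 116 days (maximum 336). A floor on the day after the last visit before omalizumab first appears is tighter. With follow-up visits 84 days apart (for example Days 365 and 449) and attended on schedule, the shift is at most 449 − 366 = 83 days.

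**7. The two cut-offs.** Under Section 4, up to about 84 days before omalizumab are lost even when the date is complete. A day-missing date moved back across a visit could lose roughly another 84.

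**The case against.** **The effect may be nil.** Neither document says that any omalizumab start is partial, or that an imputed date drives the cut; sections 2.6.1 to 2.6.10 do not cite 5.1.3. The sponsor has already placed the 17 uses after treatment, so a date inside treatment would look wrong in review. Protocol 8.2 and 8.3 provide for checks and queries before lock. Efficacy is descriptive, and the effects run in opposite directions: extra non-response lowers response rates, while removing likely relapsers flatters durability. This stands as a limit on size, and no net bias is shown. It does not remove the gap, because 5.1.3 exists for dates still partial after cleaning, and the SAP names no other date.

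**Stronger readings that the documents do not support**
- A reader might infer that the core-study reference date is the cause. For post-treatment starts it is not (step 4). Nor do the AE rules in SAP 5.1.2 avoid the problem: AE rule 3a also gives 1 January without a floor, and the AE floor based on the extension start would not bind here.
- A reader might infer that 5.1.3 always picks the earliest date. Rules 2a, 2b and 4b use mid-points; rule 2b, for example, reads "Else if the CM month is not missing, the imputed CM start date is set to the mid-month point (15MONYYYY".
- A reader might infer that valid data are certainly deleted, or that all 17 patients are affected. Only partly dated starts are at risk.
- The losses just before omalizumab cannot all be laid to imputation, since Section 4 loses such scores with complete dates too.

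**Conclusion.** The gap is real but conditional. As written, 5.1.3 can date a post-treatment omalizumab start too early by up to a month (day missing), by up to a year (month missing), or to before the core study (year missing). The cause is the absence of a floor in rule 3, together with the missing-year rule. Whether any result changes depends on two things the documents leave open: how many of the 17 dates are partial, and whether the imputed date sets the cut. If only days are missing, the effect is small, at a mean of 14.7 days. If a month or year is missing, one patient can lose Week 52 status and leave the sustained-remission group. The 54% and 4% figures rest on evenly spread starts. The conflict between section 2.6 and Section 4 holds whatever the state of the dates.

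**What to change.** In SAP 5.1.3 and 2.6.10:
1. State which omalizumab date, recorded or imputed, drives the efficacy cut.
2. Query every partial omalizumab start date.
3. Set any date still partial to the later of the calendar point (first of the month, or 1 January) and the day after the last visit before omalizumab first appears in the concomitant-medication record. For a missing year use that floor alone. Cap the result at the medication end date. Protocol Table 6-1 schedules "Ongoing Concomitant medication usage" at every visit, so the information should exist, provided the record shows the visit at which omalizumab was first entered.
4. Choose one cut-off, the start date (section 2.6) or the last visit before it (Section 4), and use it in both places.

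No change of reference date is needed for other medications: in the visible text only omalizumab triggers an efficacy cut. The cost is SAP wording, a small programming change and queries on at most 17 patients. No new data are collected.
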